## 6.0 Study Procedures

### Study protocol

After obtaining consent, study subjects will undergo the following procedures.

**COVID-19 precautions prior to and during visits.** Pre-visit phone call – we will contact the patient before all of their study visits to ask a series of COVID-19-related screening questions. Depending on their answers, we will continue with the study visit or postpone for another time. The patient will be asked to wear a face covering during all portions of their study visits in which they are in the presence of hospital staff. We will also encourage frequent hand washing and/or provide alcohol-based hand sanitizer.

Subjects will participate in a randomized, parallel-group, double-blind, placebo-controlled study in which they will receive two doses of placebo or 300 mg of lanadelumab subcutaneously. Participants will continue their usual medications throughout the study. One week (Day -7) before the administration of the first dose of the study drug, we will conduct a study visit at the hemodialysis unit. During this visit, we will give the participants a physical activity monitor to be worn for at least 5 consecutive days and will obtain baseline blood samples. During a second study visit at the dialysis unit (Day -1), we would obtain a second baseline blood sample one to three days before the administration of the first dose of the study drug. In this visit, we will also measure

muscle oxygenation using near-infrared spectroscopy (NIRS). Patients will be then asked to come to the Vanderbilt Clinical Research Center (CRC) on a non-dialysis day. During this visit (Day 0), we will obtain a detailed history, perform a physical examination, administer a quality of life (QOL) questionnaire, obtain the dialysis recovery time, and evaluate body composition and physical performance. We will then administer the first dose of the study drug and monitor the appearance of any Type I (immediate) hypersensitivity reaction for two hours before discharging patients from the CRC. We will repeat the same protocol, as outlined for Day 0 and administer the second dose of the study drug two weeks later at the CRC (Day 14).

The next two consecutive dialysis treatments after each drug administration (days 1 and 3, and days 15 and 17), we will conduct follow-up visits at the dialysis unit to collect information regarding symptoms after discharge from the CRC. During these visits, at the end of every hemodialysis session, we will also inquire, through a standardized questionnaire, about the presence of any symptoms associated with hypotension. This questionnaire will include symptoms such as cramps, dizziness, nausea, and will be scored according to the severity from 0 to 4 (none to severe). We will also collect blood samples at the dialysis unit for pharmacokinetics and special laboratory analysis. During the six-week length of the study, we will monitor the occurrence of DIH episodes and changes in blood pressure in every dialysis session. For this purpose, we will use the dialysis clinic blood pressure monitor logs. We will also conduct two additional visits at the dialysis units (Day 29 and 43) to draw blood, administer the symptomatology questionnaire, and measure blood flow with NIRS. In the final hemodialysis visit (day 43) we will also give the patients an activity monitor that will be collected after five consecutive days of continuous use. During this last visit, we will also administer the QOL questionnaire, obtain the dialysis recovery time, and perform body composition and physical performance tests (except for the six-minute walk test). Details of the study protocol can be found in Figure 5, Tables 1 and 2, and Appendix 1

### **Hemodialysis**

All subjects will be dialyzed with their usual prescription. The duration of the dialysis treatment will vary between subjects, but it will be the same as the usual standard of care. Dialysis will be performed with biocompatible polysulfone membranes (Fresenius F80-A, Walnut Creek, CA). We will use new dialyzers on each study day. Dialyzers will be stored for further analysis of the proteins adsorbed to the membrane.

Crit-Lines®, which monitors hematocrit, percent change in blood volume, and oxygen saturation during hemodialysis, will be applied every hemodialysis session during the study if the device is available and the nursing staff is trained appropriately.

### **Collection of blood samples**

Blood samples will be collected for clinical laboratory analysis in the pre-dialysis blood sample. Blood samples at the dialysis unit will also be obtained at the arterial and venous sites before dialysis, 15 minutes and one hour after dialysis initiation, and at the end of hemodialysis for research labs (e.g., markers of the kallikrein-kinin system) and pharmacokinetics analysis.

Table 1. HD study visit

• Activity monitor (Day -7 and 43)

• NIRS (Days -1, 15, 29, and 43)

• Symptomatology questionnaire

• Blood draw at the venous and arterial sites: t=0, t=15min, t=1h, t=end of HD for markers of kallikrein-kinin system and PK

----------------------------------------------------------------------------------------------------------------------------------------------------------------------------------------------------------------------------------------------------------------------------------------------------------------

### **Hemodynamic measurements**

During the baseline visit, we will obtain three supine blood pressure measurements. During hemodialysis study days, blood pressure will be taken in the arm contralateral to the access for dialysis using an automated oscillometric recording device. We will obtain three measurements during a period of 15 minutes before starting dialysis. The average of these measurements will be considered the baseline blood pressure. During hemodialysis, we will obtain blood pressure every 15 minutes. At the end of hemodialysis, we will obtain two more blood pressure measurements that will be averaged to obtain the post-dialysis blood pressure

Table2. CRC study visit

• Physical exam and history

• Body composition - physical performance tests

• QOL questionnaire/recovery time

• Study drug administration

-------------------------------------------------------------------------------------------------------------------------------------------------------------------------------------------------------------------

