## 4.0 Inclusion/Exclusion Criteria

### Study population

Participants will be recruited from Vanderbilt Dialysis Outpatient Clinics. We will enroll patients who are on maintenance hemodialysis for at least six months, with pre-dialysis blood pressure between 110 and 170 mmHg, who are being adequately dialyzed ( $Kt/V > 1.2$ ), and who are between 18 and 85 years old, who have experienced dialysis-induced hypotension (DIH) episodes at least four times in a period of 12 weeks prior to enrollment. We define DIH as the drop of systolic blood pressure (SBP) of more than 30 mmHg with associated symptoms such as nausea, dizziness, cramps, yawning, and abdominal discomfort. We will also look for nursing intervention during the hypotensive episode, but it will not be used as an inclusion criterion. Nursing intervention is defined as a temporary interruption of ultrafiltration, Trendelenburg positioning, or administration of intravenous fluids. We will exclude patients who suffered severe DIH episodes that required the use of vasopressors and the termination of hemodialysis treatment. Patients who have been hospitalized during the last three months or with clinical evidence of inflammatory or infectious disease or with severe anemia (hemoglobin less than 8 g/dl) will be excluded. Institutional review board approval and written informed consent will be

obtained from all study subjects. We expect that 60% of our subjects will be African American and 40% will be women.

*Inclusion criteria*

- Subjects age 18 to 85 years
- On thrice-weekly hemodialysis for at least six months
- Clinically stable, adequately dialyzed (single-pool Kt/V > 1.2), with polysulphone membrane for at least three consecutive months before the study
- Subjects with pre-dialytic systolic blood pressure between 110 and 170 mmHg.
- Subjects with a reduction of systolic blood pressure during hemodialysis equal to or greater than 30 mmHg, with associated symptoms such as nausea, vomiting, muscle cramps, dizziness, or anxiety.
- Hypotensive episodes should occur four times or more in four weeks (12 hemodialysis sessions).

*Exclusion criteria*

- Subjects with intradialytic hypotension that require the use of pharmacological intervention such as midodrine or vasopressin
- Subjects with pre-dialytic systolic blood pressure greater than 170 mmHg or diastolic blood pressure greater than 110 mmHg
- History of myocardial infarction or cerebrovascular event within 3 months

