## **5.0 Enrollment/Randomization**

This is a parallel study where participants will be assigned to either taking the study drug (lanadelumab) or taking the placebo (saline pre-filled syringes.) Patients will be randomly assigned to the treatment order using a permuted-block randomization algorithm. The study drug, lanadelumab, will be shipped from Takeda as pre-filled syringes along with matching placebo, also in prefilled syringes. The Vanderbilt Investigational Drug Services (IDS) will be responsible for the storage, preparation, dispensing, and labeling of the investigational agents. The Vanderbilt IDS will also maintain accurate drug storage and dispensing logs. Subjects will be randomized to receive a placebo or 300 mg of lanadelumab (Takeda Pharmaceutical, Cambridge, MA). Subjects randomized who do

not complete the whole protocol for any reason will be replaced, and their data will be analyzed separately. The half-life of lanadelumab is 14 days, and the time to reach maximum concentration is five days. For this reason, we will monitor blood pressure and the occurrence of DIH for three weeks after the administration of the second dose of the study drug.

[figure not shown]

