## **10.0 Statistical Considerations**

### ***a. Sample size***

The primary outcome will be the change in blood pressure during hemodialysis. For this, we will average blood pressure during hemodialysis of three hemodialysis sessions within the second week of treatment. Secondary endpoints will also be recorded during the second week of treatment and will include the number of hypotensive events, frequency of nursing interventions, average of dialysis recovery times, and average symptoms severity score. Based on our preliminary studies with icatibant and assuming a standard deviation of differences of 13.6 mmHg (pooled SD of the delta), a sample size of 16 in each arm will have 80% power to detect a difference in means of -13.7 mmHg, using a paired t-test with a 0.05 two-sided significance level.

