### ***b. Data analysis plan***

Standard graphing and screening techniques will be used to detect outliers and to ensure data accuracy. Distributions of the continuous outcomes will be assessed for normality. If normality is violated, proper data transformation will be applied, or non-parametric analysis methods will be considered. The primary endpoints are SBP and DBP. The secondary endpoints include heart rate, and the R-R interval (autonomic function), the time to recover after HD, symptoms associated with DIH, and the distance walked during the six-minute walk test.

Mixed effect models will be used to analyze the primary endpoint (blood pressure) with a random subject effect and with the treatment (lanadelumab vs placebo) and the time trend (measurements every 15 minutes) as fixed effects. The focus of this study will be the treatment effect and the time trend of the endpoints; however, mixed effect models also provide the flexibility of controlling for and evaluating covariates. However, we will be careful not to over-fitting the model due to the limited sample size.

Besides the above evaluation of the treatment effect and the time trend through the regression models, the direct treatment effect will also be estimated as within-subject mean difference along with their 95% confidence intervals. For the secondary endpoints, a paired t-test will be performed (lanadelumab vs placebo). If the normality of the data is violated, we will use non-parametric tests.

For binary endpoints (e.g., occurrence of hypotensive events), we will use the McNemar test to compare lanadelumab and placebo.

**Missing Data.** Based on our previous studies, we anticipate a drop-out rate of 10% or less. Subjects who drop out will be replaced. Specific inferences on effects of interest will be made by reporting a point estimate along with a 95% confidence interval and the p-value. Hypotheses will be tested at the level of  $\alpha=0.05$ . We will use SPSS (version 25.0, SPSS, Chicago, IL) and the open-source statistical package R (R Core Team, 2017) for analyses.

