## Appendix A Summary of study procedures

	+/-3 days						+/-4days				
	Day-7	Day -1	Day 0	Day 1	Day 3	Day 13	Day 14	Day 15	Day 17	Day 29	Day 43
CRC visit			X				X				
HD visit	X	X		X	X	X		X	X	X	X
Blood draw PK		X		X	X			X	X	X	X
Blood draw clinical labs	X				X	X			X	X	
Blood draw research labs		X		X				X			X
Serum pregnancy test			X				X				
Drug administration			X				X				
Medical history /PE			X								
QOL questionnaire/ recovery time			X				X				X
Symptoms questionnaire/ BP monitoring log				X	X			X	X	X	X
NIRS		X						X		X	X
Physical performance tests - Body composition***			X				X				X***
Collect dialyzer		X		X	X			X	X	X	X
activity monitor*	X*										X*

\* monitor ends after at least 5 days of consecutive use

\*\*It includes: physical performance tests (six-minute walk test, physical battery, and handgrip strength), bioelectrical impedance analysis, and MUAMC

\*\*\*Physical performance will only include handgrip strength

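### The primary analysis leaves pre-dose intradialytic blood pressure unused, so precision available from the Day -7 and Day -1 dialysis visits is lost

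*Combined protocol and SAP*

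**What the plan says.** **Design.** Section 5.0: "This is a parallel study where participants will be assigned to either taking the study drug (lanadelumab) or taking the placebo". Treatment therefore varies between patients, not within them.

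**Outcome and model.** Section 10.0 a defines the primary outcome as the blood pressure change during dialysis, averaged over three sessions in the second treatment week. Section 10.0 b states: "Mixed effect models will be used to analyze the primary endpoint (blood pressure) with a random subject effect". The fixed effects are treatment and the 15-minute time trend. Covariates are mentioned as something such models allow, with a caution about over-fitting; none is named.

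**Baseline.** Under Hemodynamic measurements in Section 6.0, three readings are taken in the 15 minutes before dialysis: "The average of these measurements will be considered the baseline blood pressure". In a week-2 session that reading is post-dose. The three supine readings at the baseline visit are resting values, not intradialytic ones.

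**Pre-dose data.** Section 6.0 and Appendix A place dialysis study visits at Day -7 and Day -1, before the first dose at Day 0. The Hemodynamic measurements text prescribes readings every 15 minutes during dialysis on study days. In Appendix A the row "Symptoms questionnaire/ BP monitoring log" is ticked only from Day 1.

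**Sizing.** Section 10.0 a: "a sample size of 16 in each arm will have 80% power to detect a difference in means of -13.7 mmHg", "assuming a standard deviation of differences of 13.6 mmHg (pooled SD of the delta"), "using a paired t-test with a 0.05 two-sided significance level".

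**The concern.** Patients enter because their pressure falls repeatedly during dialysis, and they may differ in how far and how often it falls. In a parallel trial with 16 per arm, any stable difference of that kind adds to the standard error of the treatment effect. A random subject effect accounts for the correlation among a patient's own readings, but it does not take between-patient variance out of a contrast that is itself between patients. A covariate measured before dosing can take out the part that it predicts.

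What is at stake is power and the width of the confidence interval. The pre-specified sample size has no margin, and the covariate needs no visits beyond those already scheduled. Leaving covariates open also means the choice could be made after the data are seen.

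**Working it through.** **Inputs.** From Section 10.0 a: 16 per arm, difference 13.7 mmHg, SD 13.6 mmHg, two-sided alpha 0.05, target power 80%. The SD is taken as the between-patient SD of the outcome being compared. The correlation r between the pre-dose and week-2 change is not in the documents and is assumed over a range.

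**Step 1: reproduce the plan's figure.**
- Two independent means, normal approximation: n = 2 × (1.960 + 0.842)² × 13.6² / 13.7² = 15.5, rounded up to 16 per arm. Power at 16 is 81.3%.
- Exact two-sample t (30 df): standard error = 13.6 × √(2/16) = 4.81 mmHg, noncentrality = 13.7 / 4.81 = 2.85, power 78.7%. The difference detectable with 80% power is 13.9 mmHg, and 17 per arm would be needed for 80% power at 13.7 mmHg.
- The paired t-test that the text names does not give 16. It needs 10 pairs, and 16 pairs would have 96.4% power.

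So 16 per arm is an unpaired calculation that takes no credit for pre-treatment blood pressure.

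**Step 2: ANCOVA on the change, one pre-dose covariate.** Adjusted SD = 13.6 × √(1 − r²); standard error = adjusted SD × √(2/16); noncentral t with 29 df.

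| Assumed r | Adjusted SD (mmHg) | Power for 13.7 mmHg | Detectable difference at 80% (mmHg) |
|---|---|---|---|
| unadjusted | 13.6 | 78.7% | 13.9 |
| 0 | 13.6 | 78.6% | 13.9 |
| 0.3 | 12.97 | 82.3% | 13.3 |
| 0.5 | 11.78 | 88.9% | 12.1 |
| 0.7 | 9.71 | 97.1% | 10.0 |

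**Step 3: what the table leaves out.** It charges ANCOVA one degree of freedom but not the chance imbalance of the covariate between arms. For a normal covariate this multiplies the variance on average by 1 + 1/(32 − 4) = 1.036. With that factor, power is about 77.2% at r = 0, 81.0% at r = 0.3 and 87.8% at r = 0.5. Break-even with the unadjusted test is near r = 0.2.

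**Step 4: why not a change from pre-dose.** Subtracting the pre-dose value gives SD 13.6 × √(2 × (1 − r)), if both periods have the same SD. At r = 0.3 this is 16.09 mmHg and power falls to 64.4%. At r = 0.5 it matches the unadjusted 78.7%. With r unknown, ANCOVA is the safer form.

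**The case against.** Randomisation against placebo makes the unadjusted comparison valid. Drift toward milder falls after selection is expected in both arms, and chance imbalance is already reflected in the unadjusted confidence interval. This stands: a reader might infer bias, and the documents do not support that.

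A reader might also infer that Aim 1 cannot be answered without each patient's habitual fall. Aim 1 asks whether the drug prevents the reduction in pressure, and the placebo arm answers that without pre-dose data.

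The documents do not show a large stable spread between patients. They give a total SD of 13.6 mmHg, without the between-patient share. Entry rules may also narrow the range: falls of at least 30 mmHg, pre-dialysis systolic pressure of 110 to 170 mmHg, and severe episodes excluded. Two or three pre-dose sessions may be a noisy measure, because four episodes in 12 sessions leaves eight that need not have one. All of this could lower r, and at r = 0.3 the detectable difference improves by only 0.6 mmHg (13.9 to 13.3).

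It is tempting to say that Appendix A contradicts Section 6.0. The unticked row combines symptoms with the clinic log and is not clearly the 15-minute procedure, so it shows that pre-dose recording is not explicit, no more. It is equally tempting to count the screening sessions as baseline data ("Hypotensive episodes should occur four times or more in four weeks (12 hemodialysis sessions"). No text puts those readings in the study database, and Section 4.0 also gives a 12-week window, which must be reconciled with the four-week one.

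Finally, the power figures belong to an analysis of the change. Section 10.0 b models the 15-minute readings, and a pre-dose fall need not predict their level equally well. This stands too, and is why the covariate must match the response.

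**Conclusion.** The point holds as a loss of precision. Pre-dose intradialytic pressure is within reach at two scheduled dialysis visits, the primary model does not use it, and the random subject effect is no substitute in a parallel design. The paired test and the within-subject difference in Section 10.0 b do not fill the gap either: they are framed as lanadelumab against placebo, and each patient receives only one of these.

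The size is illustrative. It rests on SD 13.6 mmHg, 16 per arm, ANCOVA on the change and an assumed r. Power rises from 78.7% to about 82% (r = 0.3) or 89% (r = 0.5). If r is zero, the cost is about 0.1 point from the lost degree of freedom, or about 1.5 points once average covariate imbalance is counted (78.7% to 77.2%). The possible loss is small beside the gain at moderate r. The documents do not establish which r applies.

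**What to change.** 1. In Appendix A, state that blood pressure is recorded during dialysis at Days -7 and -1, and taken from the clinic log for sessions between them.
2. Compute each patient's mean pre-dose value with the same formula as the week-2 outcome and, where possible, from the same source. If the second week means about Days 7 to 14, Appendix A lists only Day 13 as a dialysis study visit there, so other outcome sessions would come from clinic logs. The plan should then avoid pairing a study-device covariate with a clinic-log outcome.
3. Settle which response is primary, since Section 10.0 a describes the change and Section 10.0 b the readings. Then pre-specify, before unblinding, a single baseline covariate: the pre-dose intradialytic change if the response is the change (ANCOVA, not a change score), or the pre-dose intradialytic level if the response is the 15-minute readings. Use the systolic value for the systolic endpoint and the diastolic value for the diastolic one.

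The cost is a clarified schedule row, some log extraction and one model term per endpoint. No patients or visits are added, and one covariate respects the plan's own caution about over-fitting.

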### **Physical performance tests**

Physical performance tests will include the six-minute walk test (6MWT), physical battery (gait speed and chair stand tests), and the handgrip strength, and they will be performed as previously described. Briefly, the 6MWT consists of instructing the patients to walk back and forth on a 30-meter corridor. The distance will be recorded in meters. Handgrip strength will be assessed in both hands using a dynamometer. The mean from three consecutive efforts will be used for the analysis.

Repeated chair stands: The participants will be asked to move from a sitting position to a standing position on a 42-cm high chair as quickly as possible five times. Time to complete the five repetitions will be recorded.

Gait speed: it will be performed on a 20-meter straight path, with 5 m for acceleration, 10 m for steady state walking, and 5 m for deceleration. Time will be measured by a stopwatch as the patient reaches the markers and the end of the path. The physical battery will be evaluated using standardized tests, and the results will be scored accordingly to complete the assessment of physical performance.

